## 5. ELIDAH ELECTRICAL STIMULATION

### 5.1 Description of Device

The Elidah Elitone is an incontinence specific device that helps deliver electrical stimulation to the pelvic floor muscles transcutaneous. The design allows for home-use and wearable, ideally increasing compliance and thereby accelerating the rate of efficacy of muscle training. The device is comprised of two components: a disposable electrode and a current generator.

### 5.2 Electrode

The electrode is configured as a single unit contoured to fit against the perineal tissues with a hole in the center through which bodily fluids can pass. The skin-contacting surfaces are conductive gel regions located at the four corners with a hole in the center of the pad. Snaps and a cable is used to connect to the generator which may be worn at the waist. Benchtop testing has been completed to ensure that the resulting current passing through the Elidah electrode is similar to currently marketed 2" square patch electrodes.

Packaging: Foil pouch

Reusability: The electrode is designed to be used for one hour or less. This is an acute study and it is not expected for electrodes to be reused. A new electrode should be used for each subject.

Storage: Unused electrodes should be stored in sealable storage bag so that the gels does not dry out.

#### 5.2.1 Device Name and Identifier

Elidah Elitone (electrode)  
Identifier: EE-1002

### 5.3 Current Generator

The current generator will be used to supply the current. The generator unit, or stimulator, comprises a circuit board, rechargeable battery, and user interface, all housed within a plastic housing approximately 2" x 1.5" x 0.5". The device is programmed to deliver a variety of waveforms intended for electrical muscle stimulation. Output characteristics of the device into a 500Ω load are 0-100 volts (peak-to-peak) and 0-150mA (peak instantaneous), which is similar to numerous commercially available electrical muscle stimulation devices. The treatment intensity (i.e. voltage) is controlled by the user through a pair of increment and

decrement buttons. The device can deliver 4 twenty-minute treatments on a battery charge. Recharging of the 3.7V lithium polymer battery is achieved via conventional micro-USB to USB cable. The battery includes integrated overload protection circuitry. In addition to the increment/decrement buttons, which also serve to turn on and pause/stop the device, the user interface includes a series of colored LEDs that indicate power state, and treatment intensity. The generator includes a belt-clip to facilitate wearing the device on one's underwear or pants. The generator connects to the electrode through a custom 2-conductor cable. *The device has passed all the necessary IEC testing, including for home-use.*

### 5.3.1 Device Name and Identifier

Elidah Device (generator)  
Identifier: EC-1003

[figure not shown]
### 5.3.2 Generator Settings

- Freq: 2000Hz modulated at 50 Hz (sinewave), *Waveform B (same but square wave)*
- Timing: 6 sec on, 6s off
- Intensity: Current (mA) should be at max tolerable level, ideally to be increased, must record.

## 5b. Phase II:

In the event of successful implementation of the ultrasound protocol on women, a Phase II includes a pilot study on men. The protocol are identical with the exception of:

- Screening: Male instead of Female, pregnancy question removed
- Electrode: Is configured for male anatomy as seen in this prototype.

## 6. SAFETY ASSESSMENTS

Adverse events are the primary means for assessing safety of the device and the study subjects. All adverse events whether observed or volunteered will be recorded at every visit or during any contact such as emails or phone conversations with the subjects.

For all adverse events, sufficient information will be pursued and/or obtained so as to permit 1) an adequate determination of the outcome of the events (i.e., whether the effect should be classified as a serious adverse effect) and; 2) an assessment of the casual relationship between the adverse event and the investigational device or, if applicable, the other study treatment or diagnostic product(s).

Adverse event or abnormal test findings felt to be associated with the investigational device or, if applicable, other study treatment or diagnostic product(s) will be followed until the event or the abnormal finding resolves or stabilizes at a level acceptable to the investigator and sponsor.

## 6.1 Risks and Side Effects

The risks to those in the study will be similar to other transcutaneous electrical nerve stimulation (TENS) patches. Much of the known warnings and cautions of electrical stimulation with electrodes will be avoided due to the location-specific nature of the SUI device. However possible side effects may be:

- Electrical shock or pain
  - The generator is powered by a 3.7 Volt battery. Tampering with the generator or the electrode may cause damage to the circuitry and result in mild shock. There is no reason to tamper or open any component during this study.
  - The device is not meant to be used in water or during urinating. If exposed to liquids, the device may result in mild shock. If any component is exposed to a liquid please contact the research staff and investigator immediately.
- Pain on surface if the gel to skin contact is not secure.
  - If the device is not properly attached to the treatment site, the electrode may contact the skin directly. This may present as an uncomfortable burning or tingling sensation for the subject. In this event, a subject should turn off the device, remove the electrode and inspect the electrode for disconnections between the gel and electrode. If no issues are found, the subject should reapply the electrode and ensure that it securely contacting the skin at all points.
- Skin irritation (redness, sensitivity, etc.)
  - The electrodes used in this study are very similar to the electrodes currently on the market for TENS and other electrical devices. The gel which contacts directly with the skin may cause sensitivity or irritation to some subjects due to unique skin sensitivity.
  - With any adhesive that contacts the skin, redness or sensitivity may be present after removal of the electrode. This is a normal activity; such as redness experienced after removing a bandage. If recurring redness or sensitivity occurs, the subject should contact the study staff.

To minimize the risk, emphasis in the Instructions for Use will be placed on good skin contact/adherence. This risk is reasonable and similar to standard TENS electrode patches. The FDA considers similar device to have low risk: "*Nonimplantable Electrical Incontinence Devices are a Non-significant risk device, no IDE needed*". We do not foresee any psychological, financial, legal or other risk to subject associated with the study, except confidentiality which we address in other sections.

The intensity of the current/voltage of the device is modulated by the subject and not prescribed. The intensity will also start from 0 and incrementally increase with each level pressed by the subject. The above are known side effects with electrical stimulation devices and are not considered severe adverse events, nor unanticipated problems. It is possible that participants use this device improperly, or place it at an improper location. The electrode nor the generator may be applied while the subject urinates.

Loss of confidentiality represents an adverse event, however, we will take several steps to minimize the risk of breaching participant confidentiality/privacy, as described above.

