## 6.3 Reporting Procedures

Adverse events will be reported from the clinical site to the sponsor within 24 hours.

The sponsor will use the following 0 to 4 scale to grade adverse events (AE): 0 = none or event is not clinically significant, 1 = mild AE that does not require treatment, 2 = moderate AE that does require treatment, but resolves completely and 3 = severe AE, e.g., results in temporary inability to conduct one or more everyday activities and requires ongoing medical attention, and 4 = life threatening or results in permanent inability to conduct one or more everyday activities.

In the event of an adverse event to a subject in the proposed study, the site investigator will discuss the available medical treatment options with the subject. If an AE occurs, the Sponsor will assist the subject in obtaining appropriate medical attention if unable to be performed by the Investigator. If treatment or hospitalization is required as a result of participation in this study, the subject and their insurance carrier are responsible for the cost of medical care. The subject will not lose any of their legal rights and they do not release the Sponsor, investigators, the study staff, or study site from liability for mistakes or intentional misconduct by participating in the study.

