## 6.4 Followup for Adverse Events

The Investigator will follow up moderate and severe adverse events until it is resolved/stable. The study sponsor will be notified when the issue has been resolved.

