### 8.3 Interim Analyses and Stopping Rules

The study is small and acute, and so was purposely designed to avoid any interim analyses from occurring. In the event of a SAE with direct correlation to the device, the study will be temporarily halted until the safety issue can be addressed. Only 1 SAE will trigger this halting in enrollment. Due to the small enrollment size, the number of unanticipated problems or adverse events will not spur an interim analysis or early end to the study.

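### Section 6.1 labels the listed device effects by type as not severe and not unanticipated, which conflicts with the consequence-based 0–4 grading in section 6.3

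*Combined protocol and SAP*

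**What the plan says.** Section 6.1 lists three kinds of possible side effect: "Electrical shock or pain", pain at the surface when gel contact is not secure, and skin irritation. Its closing text then classifies them together: "The above are known side effects with electrical stimulation devices and are not considered severe adverse events, nor unanticipated problems".

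Section 6.3 has the sponsor grade adverse events from 0 to 4 by what the event leads to. Grade 2 is a moderate event that needs treatment but resolves fully. Grade 3 reads "3 = severe AE, e.g., results in temporary inability to conduct one or more everyday activities and requires ongoing medical attention". Grade 4 is a threat to life or a permanent inability. Nothing in the scale exempts the effects listed in 6.1.

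Four other rules bear on the point:

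- **Reporting (6.3):** "Adverse events will be reported from the clinical site to the sponsor within 24 hours".
- **Follow-up (6.4):** "The Investigator will follow up moderate and severe adverse events until it is resolved/stable". The opening text of section 6 separately requires events thought to be device-related to be followed until they resolve or stabilise, with no condition on severity.
- **Seriousness (6.2):** defined by outcome, namely death, threat to life, hospitalization, lasting disability or congenital anomaly.
- **Halting (8.3):** an SAE directly correlated with the device halts the study temporarily, and the threshold is one: "Only 1 SAE will trigger this halting in enrollment".

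**The concern.** Severity and expectedness are judgements about an individual occurrence. Section 6.1 makes both in advance for a whole class of events, and the class consists of the effects that the plan itself foresees from the device. If that sentence is applied as written, a listed reaction with grade 3 consequences is reported as non-severe and anticipated, whatever happened to the woman.

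Section 6 calls adverse events the main means of assessing safety. With 8 women planned, 12 at most and 5 at least, the label on one event can decide how the safety summary reads. What is at stake is the classification of an event. Its capture is not in doubt.

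**Working it through.** The plan states no figure on this point, so the check is mainly textual.

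**Step 1. One event under both rules.** Take a hypothetical skin reaction under the electrode that temporarily prevents an everyday activity and needs continuing medical attention.

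| Rule | Basis | Result |
|---|---|---|
| 6.1, closing text | type of event: skin irritation is listed | not severe, not unanticipated |
| 6.3 | consequence | grade 3, severe |
| 6.2 | outcome | serious only if one of the listed outcomes occurs |
| 6, opening text | association with the device | followed until resolved or stable |
| 6.3, reporting | any adverse event | to the sponsor within 24 hours |

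The first two rows contradict each other, and no passage gives either one precedence.

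**Step 2. Does another grade absorb the event?** Grade 2 requires complete resolution. An event needing ongoing attention does not clearly fit, so if it is barred from severe it has no clear grade.

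**Step 3. Is the 6.1 list confined to mild forms?** For shock, yes: tampering "may cause damage to the circuitry and result in mild shock", and contact with liquid is described in the same way. Surface pain is described differently: "This may present as an uncomfortable burning or tingling sensation for the subject". That has no upper limit. The skin irritation item likens redness after removal to that from a bandage, but its heading is open-ended. The pain and skin items are therefore not limited to mild forms. Section 5.3.2 also sets intensity at the highest tolerable level, and section 4.4 allows a further increase on the repeat test.

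**Step 4. Halting.** The trigger in 8.3 is an SAE, and 6.2 defines an SAE by outcome. Neither severity nor expectedness enters that definition. The link to 6.1 exists only if severe there was meant as serious. The terms are used loosely enough to leave the question open: 6.1 pairs severe events with unanticipated problems, 8.3 discusses SAEs alongside unanticipated problems, and the opening of section 6 speaks of a serious adverse effect.

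**Step 5. Wording of 6.4.** It names moderate and severe events, which are the labels of grades 2 and 3. Grade 4 carries neither label, so a literal reading does not name the highest grade.

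**Step 6. Scale.** Let n be the number of women, and use exact (Clopper-Pearson) 95% intervals. For 0/n the upper limit is 1 − 0.025^(1/n).

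| n | One event labelled severe | Same event not labelled severe |
|---|---|---|
| 8 | 1/8 = 12.5% (0.3% to 52.7%) | 0/8 (upper limit 36.9%) |
| 12 | 1/12 = 8.3% (0.2% to 38.5%) | 0/12 (upper limit 26.5%) |

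The documents give no rate for such events. Under assumed true rates p, the chance of at least one is 1 − (1 − p)^n:

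| p (assumed) | n = 8 | n = 12 |
|---|---|---|
| 1% | 7.7% | 11.4% |
| 5% | 33.7% | 46.0% |
| 10% | 57.0% | 71.8% |

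**The case against.** The strongest reply is that 6.1 describes risks while 6.3 is the operative procedure. On that view the sentence only says that the mild, familiar forms just described are not severe, and 6.3 still governs any actual event. This is a fair reading, and nothing in the text rules it out. But nothing states it either, and the mild wording is attached only to the shock examples (step 3). The ambiguity remains.

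A reader might also draw stronger conclusions that the documents do not support:

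- **That 6.1 overrides 6.3 and fixes the severe count at zero.** No precedence is stated. The count is zero for listed effects only if 6.1 is the rule applied.
- **That follow-up is lost.** The opening of section 6 follows device-associated events whatever their grade, so only the 6.4 route is touched.
- **That the halting rule is disabled.** Read literally, 6.1 does not reach the SAE definition. Section 7 also allows a pause for a serious device issue such as a hospitalization, although it is worded as a possibility. The label of unanticipated problem drives no stopping rule, because 8.3 says the number of such problems will not end the study early.
- **That the safety conclusion is favourable by construction.** All adverse events are recorded, and section 9.3 has a safety board review them. Section 8.4 lists no severe-event count among the primary or secondary outcomes.

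It is also fair to say that 1/8 and 1/12 are simply the share of any one participant. They show what one label is worth in a study of this size and do not measure how often the sentence would matter.

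**Conclusion.** The conflict between 6.1 and 6.3 is real and limited to classification. A listed reaction that met grade 3 would receive opposite severity labels, and could be reported as non-severe and anticipated. One such relabelled event moves the severe proportion from 12.5% to 0% with 8 women, or from 8.3% to 0% with 12.

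This rests on two assumptions: that a listed effect reaches grade 3, for which the documents give no rate, and that whoever classifies it applies 6.1 as written. Any effect on the one-SAE halt needs a third, that severe in 6.1 means serious.

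The point should be corrected before enrolment. It is more than missing detail, because the plan contains a stated rule that mislabels an event if it is followed.

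**What to change.** Reconcile 6.1 with 6.2 and 6.3 by replacing the sentence in 6.1 with text along these lines: *The effects above are expected in nature. Being listed informs the assessment of expectedness only. Each occurrence is graded on the scale in section 6.3 and assessed for seriousness against the criteria in section 6.2 on its own facts.*

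In addition:

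- State whether severe in 6.1 refers to severity or to seriousness, so that its relation to the halting rule in 8.3 is clear.
- In 6.4, refer to the 6.3 grade numbers instead of the words moderate and severe, so that the place of grade 4 is explicit.

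The cost is one sentence replaced, one clarification and a wording check in 6.4. Procedures and sample size do not change. The small downside is that the safety summary may look slightly less favourable.

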### Other Safety Considerations:

The device turns off automatically after 20 minutes however, it should not be left on for extended periods of time. The device cannot be used while charging. The device is not a life-sustaining device if it fails and stops working. The electrode cannot be used with standard generators due to a non-typical connector.

## 6.2 Adverse Events and Serious Adverse Events

An **adverse event (AE)** is generally defined as any unfavorable and unintended symptom or sign which either occurs during the study, having been absent at baseline, or if present at baseline, appears to worsen. Adverse events are to be recorded regardless of their relationship to the study intervention.

A **serious adverse event (SAE)** is generally defined as any untoward medical occurrence that results in death, is life threatening, requires insubject hospitalization or prolongation of existing hospitalization, results in persistent or significant disability/incapacity, or is a congenital anomaly. Solicited adverse events will be collected at the office visits.

## 6.3 Reporting Procedures

Adverse events will be reported from the clinical site to the sponsor within 24 hours.

The sponsor will use the following 0 to 4 scale to grade adverse events (AE): 0 = none or event is not clinically significant, 1 = mild AE that does not require treatment, 2 = moderate AE that does require treatment, but resolves completely and 3 = severe AE, e.g., results in temporary inability to conduct one or more everyday activities and requires ongoing medical attention, and 4 = life threatening or results in permanent inability to conduct one or more everyday activities.

In the event of an adverse event to a subject in the proposed study, the site investigator will discuss the available medical treatment options with the subject. If an AE occurs, the Sponsor will assist the subject in obtaining appropriate medical attention if unable to be performed by the Investigator. If treatment or hospitalization is required as a result of participation in this study, the subject and their insurance carrier are responsible for the cost of medical care. The subject will not lose any of their legal rights and they do not release the Sponsor, investigators, the study staff, or study site from liability for mistakes or intentional misconduct by participating in the study.

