- Verify that source documents and trial records are accurate, complete, and up to date
- Determine whether all adverse events are appropriately reported within time periods required
- Communicate deviations from the protocol and make appropriate actions.

In addition, a Data Safety and Monitoring Board will be established for this project and will review the study design, IRB protocol, adverse events and findings of the study.

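### Section 6.3 gives severity grading of adverse events to the sponsor, with no investigator grade, and no one is named to judge relation to the device

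*Combined protocol and SAP*

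**What the plan says.** Section 6 makes adverse events the main means of assessing safety and requires all of them to be recorded. Section 6.3 then sets the route: "Adverse events will be reported from the clinical site to the sponsor within 24 hours". The next paragraph names the grader: "The sponsor will use the following 0 to 4 scale to grade adverse events (AE". Grade 0 covers both no event and an event that is not clinically significant, and grade 1 is a mild event needing no treatment. The scale continues "2 = moderate AE that does require treatment, but resolves completely and 3 = severe AE", where severe is illustrated by temporary loss of everyday activities with ongoing medical attention. It ends with "4 = life threatening or results in permanent inability to conduct one or more everyday activities".

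There are two follow-up rules. Section 6 covers events by relation to the device: "Adverse event or abnormal test findings felt to be associated with the investigational device" (or with other study products) are to be followed until they resolve or settle at a level that both investigator and sponsor accept. Section 6.4 covers events by severity: "The Investigator will follow up moderate and severe adverse events until it is resolved/stable".

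Section 8.3 adds a halt: "In the event of a SAE with direct correlation to the device, the study will be temporarily halted". Section 9.3 has the sponsor's clinical director oversee safety data collection. It also sets up a monitoring board that "will review the study design, IRB protocol, adverse events and findings of the study".

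**The concern.** The party that grades severity has an interest in the result. Section 2.2 presents the device as the company's own product, and Section 8.1 ties the sponsor to its further development. The study is single-arm and unblinded (Section 3.9), so the grader knows that every event occurred with the device. The sponsor does not examine the subject, while the clinician who does is given no grade to record.

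At stake is the credibility of the severity information. If only the sponsor's grade is kept, a reader of the results cannot tell whether the examining clinician would have agreed. An event that was reported but scored 0 cannot be told apart, by its grade, from no event. The judgement of relation to the device matters as much, because a follow-up rule and a study halt both depend on it, and it has no named owner.

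**Working it through.** No arithmetic applies: the point concerns who makes which judgement. I compared the sections on recording, grading, relation to the device, follow-up and oversight.

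1. **Severity.** Section 6.3 names the sponsor. Sections 6, 6.1, 6.2, 6.4, 8.3 and 9.3 give the investigator no severity grade. None of them provides for a second grade, a rule for disagreement, or a time limit for the sponsor's grade. Sole sponsor grading is therefore a stated rule, not a silence.

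2. **Facts the grade needs.** Grades 1 and 2 are separated by whether treatment is required. Grade 2 also requires complete resolution. Grades 3 and 4 turn on medical attention, threat to life and loss of everyday activities. The site learns these facts first; Section 6.3 itself has the site investigator discuss treatment options with the subject.

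3. **Grade 0.** One code serves two states, no event and an event judged not clinically significant. Under Section 6.3 the sponsor makes that judgement.

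4. **Relation to the device.** Section 6 requires enough information to assess the causal relationship, but it is written in the passive and names no assessor. Its follow-up rule covers events felt to be associated with the device, without saying by whom. The halt in Section 8.3 needs a serious event correlated with the device, again with no assessor. Section 7 comes nearest: it allows a pause if the sponsor discovers a serious problem with use of the device. It does not assign the event-level judgement.

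5. **Seriousness.** Section 6.2 defines it by outcomes such as death or hospitalisation. The 0 to 4 grade enters neither that definition nor the halt.

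6. **Follow-up.** Setting the two rules beside the scale:
   - An event felt to be device-associated is followed under Section 6 at any grade, including 0 and 1, and the end point is joint.
   - An event not felt to be associated with the device or another study product is followed only if Section 6.4 applies. That section uses the words moderate and severe. The only definitions of those words are grades 2 and 3 in Section 6.3, but Section 6.4 does not cite the scale or say whose grade counts.
   - Grade 4 carries neither label, so Section 6.4 read literally does not name it.
   - Grade 2 includes complete resolution, which is known only once an event has been followed, yet Section 6.4 uses the label to decide what is followed.

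   The three sections do not fit together as written.

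**The case against.** The strongest reply is that the safeguards are wider than Section 6.3 alone suggests and that the study is a small, single-sitting pilot (goal of 8 subjects, at most 12). All events are recorded whatever their grade or relation. The sponsor grades from facts the site reports, source records are checked, and a board reviews adverse events. The investigator is equally unblinded and works under a contract with the sponsor (Section 7), so moving the grade does not remove all interest. These points stand and limit the seriousness of the concern. They do not supply the missing investigator grade or name who judges relation.

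A reader might go further and infer four things that the documents do not support:

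- *That the sponsor's grade decides which events are followed.* Section 6 requires follow-up of device-associated events at any grade, and Section 6.4 does not say whose grade applies. At most, the grade could matter for events not felt to be related to a study product.
- *That the sponsor controls the whole safety classification.* Seriousness and the halt do not use the 0 to 4 grade, and the judgement of relation is unassigned. Sponsor control of that judgement is neither shown nor excluded.
- *That the board sees only the sponsor's grade.* Section 9.3 does not say what the board receives.
- *That the bias can be expressed as a change in a moderate-event rate.* No such rate is planned. The outcomes in Section 8.4 are movement and muscle identification, and regrading an event leaves the count of recorded events unchanged.

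**Conclusion.** The concern holds for severity grading and for the unassigned judgement of relation to the device. Section 6.3 gives the 0 to 4 grade to an interested party, with no grade from the clinician who saw the subject and no means of showing disagreement. Its reach is every adverse event in the study, but its numerical effect cannot be estimated from the documents. For follow-up the conclusion is narrower: Sections 6, 6.3 and 6.4 are not consistent and must be reconciled.

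This rests on two assumptions: that the sponsor is the company developing the device, as Sections 2.2 and 8.1 together indicate, and that no separate form already collects an investigator grade. The appendices are separate documents; the two listed are the screening checklist and the consent form. The matter is worth correcting before enrolment. It does not undermine the movement endpoint.

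**What to change.** In Section 6.3, have the investigator record three items in the existing 24-hour report: severity on the 0 to 4 scale, seriousness under the Section 6.2 definition, and relation to the device. State that the investigator's judgement of relation is the one recorded for Sections 6 and 8.3. If the sponsor also grades, keep its grade as a separate second entry. Report both grades and give both to the board in Section 9.3. An event scored 0 by one party and higher by the other then stays visible.

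Reconcile Section 6 (follow-up by relation to the device), Section 6.3 (the scale) and Section 6.4 (follow-up by severity). The revised text should say whose grade Section 6.4 means, how the two follow-up rules fit together, and how grade 4 is treated. Which follow-up rule should apply is for the authors to decide.

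The cost is a few sentences, three fields on the adverse event form, and occasional disagreement between grades that has to be shown. No extra visits or staff are needed.

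### Grade 0 of the adverse event scale means either no event or an event judged not clinically significant, so a recorded minor reaction can carry the code for no event

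*Combined protocol and SAP*

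**What the plan says.** Section 6 gives adverse events the leading role in the safety assessment: "Adverse events are the primary means for assessing safety of the device and the study subjects". It asks that all of them be recorded, whether staff observe them or the participant volunteers them.

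Section 6.2 defines an adverse event broadly, as an unfavourable and unintended sign or symptom that is new or worse than at baseline. It sets no minimum of clinical importance and adds: "Adverse events are to be recorded regardless of their relationship to the study intervention".

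Section 6.3 gives the grading to the sponsor, on a scale from 0 to 4. The two lowest grades are "0 = none or event is not clinically significant" and "1 = mild AE that does not require treatment". The protocol does not say what makes an event clinically significant.

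Section 6.1 lists the reactions to be expected: shock or pain, surface pain from poor contact, and skin irritation. On irritation it says that "redness or sensitivity may be present after removal of the electrode. This is a normal activity".

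**The concern.** One code has two meanings. A woman with no event and a woman with a recorded event that the sponsor considers unimportant can both be coded 0. The scale also gives a grader no way to choose between 0 and 1 for a slight reaction that needs no treatment, because both descriptions fit it.

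This matters because the study is a single sitting with few women and a surface electrode. Slight local reactions are the events the protocol itself leads one to expect, and they lie on this boundary. If results are summarised by grade, the split between women with a minor reaction and women with none depends on an undefined judgement made by the device's sponsor.

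**Working it through.** The plan states no figure to reproduce. The check sets the definitions side by side and then works out how much one coding decision can move a result.

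**1. Event definition against grade 0.** Section 6.2 has no significance threshold, but grade 0 in section 6.3 introduces one. An event below that threshold is still an adverse event under 6.2 and must still be recorded under section 6. It then receives the grade that also stands for no event. The two sections do not fit together.

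**2. Grade 0 against grade 1.** Take transient redness after the electrode comes off.

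- It needs no treatment, so it fits "1 = mild AE that does not require treatment".
- Section 6.1 calls such redness or sensitivity normal, so a grader could also judge it not clinically significant and code it 0.
- Neither choice would breach the protocol. Two graders could code the same event differently and both be within the text.

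**3. What depends on the choice between 0 and 1.**

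| Provision | What it depends on | Changed by 0 versus 1? |
|---|---|---|
| Recording (sections 6 and 6.2) | Meeting the event definition | No |
| Reporting from site to sponsor within 24 hours (6.3) | Being an adverse event | No |
| Follow-up in section 6 | Association with the device, treatment or diagnostic product | No |
| Follow-up in section 6.4 | Being moderate or severe | No |
| Halt in section 8.3 | One serious event directly correlated with the device | No |
| Any summary by grade | The grade | Yes |

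**4. Size of one coding decision.** Section 3.3 gives a goal of 8 women, a minimum of 5 and a maximum of 12. If a woman's only recorded event is coded 0, and grade 0 is read as no event, the proportion of women with a graded event is lower by 1/n:

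- n = 5: 1/5 = 20 percentage points
- n = 8: 1/8 = 12.5 percentage points
- n = 12: 1/12 = 8.3 percentage points

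The step is per woman, not per event. A second event in a woman already counted does not move the proportion. The documents give no expected frequency of skin reactions, so the number of women affected cannot be estimated from them.

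**The case against.** The strongest reply is that grade 1 already exists and describes a slight untreated reaction well. A reader might infer from grade 0 that the expected mild reactions will be graded as if nothing had happened. The documents do not support that, because nothing assigns those reactions to grade 0. Section 6.1 calls only redness or sensitivity after removal normal. It lists pain as a possible side effect without calling it normal. It then says the listed effects do not count as severe events or unanticipated problems, which rules out severe but not mild. This reply stands, and it limits the point to an undefined boundary.

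A second reply is that no event is lost. All are recorded, the clinical director checks that they are properly reported, and section 9.3 provides for a data safety and monitoring board that reviews them. The number of women with any recorded event can be counted whatever the grades. This also stands. A reader might infer that the device will be made to look free of reactions, but that goes beyond the text. The plan specifies no table by grade and no rule that counts only grade 1 and above. Sections 8.4.1 and 8.4.2 list no safety outcome, and sections 9.2 and 9.4.3 defer the analysis to a statistical analysis plan still to be written. The same silence means that nothing in the plan secures a count of women with any event.

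A reader might also object that no grade names death, since the top of the scale is "4 = life threatening or results in permanent inability to conduct one or more everyday activities". Section 6.2 already classes death as a serious adverse event, and section 8.3 halts the study if one such event is directly correlated with the device. In a single-sitting study this gap is minor and is not pressed.

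**Conclusion.** The point holds in a limited form. Grade 0 in section 6.3 conflicts with the event definition in section 6.2 and overlaps with grade 1, so a recorded minor reaction may be coded 0 or 1 at the sponsor's undefined judgement. The consequence is confined to the safety summary.

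The possible shift of 8.3 to 20 percentage points per woman recoded, for 12 down to 5 women, rests on two assumptions: that the summary is made by grade, with 0 read as no event, and that the woman has no other event graded 1 or higher. The documents neither state nor rule out such a summary. Undercounting is therefore a risk left open by the plan, not an established outcome. The change is still worth making, because it costs almost nothing and takes the judgement out of the summary.

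**What to change.** In section 6.3 and in the grading key of the case report form:

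- Reserve 0 for no adverse event.
- Grade every recorded adverse event at least 1, and state that grade 1 includes events judged not clinically significant, such as redness after electrode removal when it is recorded as an adverse event.
- In the statistical analysis plan still to be written, report the number of women with any recorded adverse event alongside the distribution of grades.

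If the sponsor wants to keep its view on clinical significance, it can be a separate yes/no item that does not alter the grade.

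The cost is a few lines of text. No procedure, follow-up rule or halting rule changes. The downside is that the reported event rate may look slightly less favourable, by the steps given above for each woman recoded. The change is best made before the first event is graded.
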